5.2 Primary Safety Endpoints

The primary safety endpoint is the rate of device-related adverse events. It will be calculated as the number of participants with adverse events related to device divided by total number of participants. Adverse events related to device is determined by the responses to “Relationship to study device” on the “Adverse Events” log form:

- Likely Related
- Related

95% confidence interval will be calculated using Clopper-Pearson exact method. The analysis will be performed on the enrolled population.

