## 5 STUDY POPULATION

### 5.1 Inclusion Criteria

In order to be eligible to participate in this study, an individual of any age or gender, must meet all of the following criteria:

1. Has an eligible vascular access device in situ or will have one placed with needle-free connectors  
Note: This covers all needle-free devices, including central venous catheters, peripheral IV catheters and arterial VADs
2. Is expected to receive VAD therapy for a minimum of 3 days
3. Is expected to be available for regular observation from consent until end of study.
4. Able and willing to provide informed consent or legal authorized representative (LAR)\* authorized to give consent on behalf of the participant.

\*LAR not applicable for AT01

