2.1 Study Design

This is a multi-center, single-arm, prospective post-market study that will enroll up to 175 participants in order to have 150 evaluable participants who have vascular access devices as part of their routine medical care. Data related to the safety and performance of the BD PureHub™ Disinfecting Cap will be captured when used as intended.

Participants will be screened against eligibility criteria and will be considered enrolled once the informed consent document is signed. Each study participant will have a BD PureHub™ Disinfecting Cap attached to each eligible needle-free connector to one or more VADs by a clinician. Clinicians will then be advised to place subsequent BD PureHub™ Disinfecting Caps as per the Instructions for Use through the course of the participant's IV therapy. During this time, attachment and removal success will be captured, as well as any device-related adverse events (AEs).

Participants will be followed from the time of enrollment until one week post VAD therapy, department/hospital discharge or 45 days post enrollment date, whichever comes first. Participants, with a VAD in place, who will be discharged from the hospital, but return regularly for catheter access to the site will remain in the study, either until the 45 days are reached or the VAD therapy is ended. If the catheter access will not be performed at the clinical trial site, the participant cannot continue in the study.

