2.8 Acceptance Criteria

There are no acceptance criteria for the study device.

3 Intended Statistical Software and Data Information

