4.1 Population Definitions

Enrolled: All participants who sign the ICF.

Evaluable: All enrolled participants who have at least 1 BD PureHub™ Disinfecting Cap applied.

5 Statistical Analysis/Calculations

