5.1 Primary Performance Endpoints

The primary performance endpoints are:

- Attachment success rate of the BD PureHub™ Disinfecting Caps to a needle-free connector
- Removal success rate of the BD PureHub™ Disinfecting Caps to a needle-free connector

The attachment success will be performed on enrolled population with non-missing data on PureHub Initial Placement CRF page. The removal success will be performed on evaluable population.

If the clinician can successfully attach the first BD PureHub™ Disinfecting Cap, it is considered as attachment success. Attachment success will be based on count of “Yes” responses to the following fields in the CRF pages:

- PureHub Initial Placement page, Attachment success is “Yes”
- PureHub Maintenance page, Attachment success is “Yes”

The attachment success rate will be computed as the number of successful attachments divided by the total number of attachments. The total number of attachments can be calculated using the following CRF pages:

- PureHub Initial Placement page, Attachment success is “Yes” or “No”

- PureHub Maintenance page, Attachment success is “Yes” or “No”.

The removal success rate will be computed as the number of successful removals divided by the total number of removals.

Removal success will be based on counts of “Yes” response to “Removal success” question in the “PureHub Maintenance” CRF page. Total number of intended removals will be based on the number of times the “Removal Success” response is chosen (regardless of “Yes” or “No”).

95% confidence interval will be calculated for both rates using the Clopper-Pearson exact method.

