5.3 Informational Endpoint(s)

The informational endpoints are:

- The number of BD PureHub™ Disinfecting Caps used per day/per study participant
- The purposes for each intended removal of the BD PureHub™ Disinfecting Cap from the needle free connector
- Incidence of central line associated bloodstream infection (CLABSI)
- Incidence of bloodstream infections

The calculation of number of PureHub caps used per day will be total number of caps used (including the ones attempted but didn’t attach) divided by number of days participants were in VAD therapy. If multiple VADs were removed, number of days will be last VAD removal date – PureHub initial placement date. If at least one VAD is not removed, the number of days will be the minimum of study duration (participant end of study date – PureHub initial placement date) and 45 days. The number of caps used will be from the following CRF pages:

- PureHub Initial Placement page, Number of caps used
- PureHub Maintenance page, Number of caps used

The purposes of removal of the BD PureHub™ Disinfecting Cap are identified on “PureHub Maintenance” log in response to “Removal reason” question. The percentage of each response will be provided, and the denominator will be the total number of intended removals.

Incidence of bloodstream infections can be identified on the CRF “Adverse Events” log form. If response to “In case of bloodstream infection, how was it confirmed” is not “Blood Stream Infection Not Present”, then subject had a bloodstream infection.

Central line associated bloodstream infection can be identified if the response to “Is the bloodstream infection central-line associated” is “Yes” on the CRF “Adverse Events” log form.

The analysis will be performed on the evaluable population. Descriptive statistics for the informational endpoints will be provided. Summary statistics for categorical variables will include frequency counts and percentages and for continuous variables will include mean, standard deviation, minimum, median, and maximum.

6 Summary of General Study Data

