6.6 Device Deficiency

Device deficiencies will be tabulated and presented on participant level for evaluable population. Details regarding device deficiencies will be listed.

7 Safety Analysis

An AE is defined as any untoward medical occurrence, unintended disease or injury, or untoward clinical signs (including abnormal laboratory findings) in participants, users or other persons, whether or not related to study device and whether anticipated or unanticipated (ISO 14155:2020). In this study, AE collection will be limited to those events judged to be related or likely related to the BD PureHub™ Disinfecting Cap and any events of bloodstream infection, including central line associated bloodstream infections (as defined in the List of Abbreviations).

An overall summary including the number and percentage of subjects with at least one AE, total number of AEs, total number of SAEs, AEs by relationship to the Study Device/Procedure, and AEs by severity of the event will be summarized for the enrolled population. In addition, AEs will be summarized by System Organ Class (SOC) and Preferred Term (PT):

- Number of AEs by SOC and PT
- Number of SAEs by SOC and PT
- Number of AEs by relationship to study device/procedure
- Number of AEs by severity by SOC and PT

A listing of all AEs, SAEs and UADEs will be provided for the enrolled population. An UADE is identified if answer to the question “Is the event expected” on the Adverse Events CRF page is “No”.

8 Interim Analysis Plan

No interim analysis is planned for the study.

9 References

None.

10 SAP Revision History

Version Number	Rationale for Change	Section or Page Affected	Description of Change
1.0	Original SAP		
2.0	Amendment	Section 5.3, page 8	Updated methodology for calculating number of caps per day
3.0	Amendment	Section 5.3, page 8	Updated methodology for calculating number of caps per day. The number of days for subject in study will be capped at 45 days.

11 Appendix

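### The primary device-related AE rate is divided by everyone who signed consent, so any participant who never had a cap applied or attempted lowers the rate and its upper confidence limit

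*SAP*

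**What the plan says.** SAP 5.2 divides the number of participants with an AE rated Likely Related or Related to the device by the total number of participants, with a 95% Clopper-Pearson interval. It then fixes the population: "The analysis will be performed on the enrolled population". SAP 4.1 gives the definition: "Enrolled: All participants who sign the ICF". No exposure to the cap is required. Protocol 10.5 gives the same ratio and names no population.

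Consent can come before there is anything to cap. Inclusion criterion 1 in Protocol 5.1 reads "Has an eligible vascular access device in situ or will have one placed with needle-free connectors", and the notes to Table 1 of the protocol allow initial placement on a later day than baseline. SAP 2.1 says the study "will enroll up to 175 participants in order to have 150 evaluable participants", and evaluable differs from enrolled only in requiring at least one cap applied.

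Other analyses in the SAP do carry an exposure condition. For attachment, SAP 5.1 says "The attachment success will be performed on enrolled population with non-missing data on PureHub Initial Placement CRF page". Removal success (5.1), the bloodstream infection summaries (5.3) and device deficiencies (6.6) use the evaluable set. The general AE summary in SAP Section 7 does not: "AEs by severity of the event will be summarized for the enrolled population".

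**The concern.** The primary safety figure should describe risk in people in whom the cap is used. A participant with no cap applied or attempted cannot enter the numerator, and Table 1 schedules no device-related AE assessment before initial placement. That participant is not an observed non-event, yet SAP 5.2 counts one. Every such participant pulls the rate down when there are events, and pulls the upper limit down even when there are none. The error cannot go the other way.

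This is also the only primary endpoint without an exposure condition. A bloodstream infection judged related to the cap would be divided by evaluable participants in SAP 5.3 and by enrolled participants in SAP 5.2.

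With no comparator and no performance threshold (SAP 2.8: "There are no acceptance criteria for the study device"), the estimate and its interval are the whole safety result, so the denominator should be right.

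**Working it through.** **The plan's own figures.** The safety part of the sample-size section (SAP 2.4, Protocol 10.2) uses n = 150, which is the evaluable target:

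- 1 − 0.99^150 = 77.9% (stated 78%)
- 1 − 0.98^150 = 95.2% (stated 95%)

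Both reproduce. The detection probabilities are therefore computed on the number planned to have a cap applied, while the endpoint is computed on the number consented.

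**Inputs.** Exposed participants: E = 150 (planned evaluable number, SAP 2.1). Maximum enrolment: 175 (SAP 2.1). Interval: two-sided 95% Clopper-Pearson (SAP 5.2). The number unexposed, u, and the number of participants with an event, x, are not in the documents. They are assumptions, shown over a range.

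**Dilution of the rate.** For x ≥ 1, the ratio of the enrolled rate to the exposed rate is [x/(E + u)] ÷ [x/E] = E/(E + u). The relative reduction is u/(E + u), whatever x is:

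- u = 3: 3/153 = 2.0%
- u = 10: 10/160 = 6.3%
- u = 25: 25/175 = 14.3%

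**Effect on the interval.** With x = 0 the point estimate is 0% for any denominator, and the upper limit is 1 − 0.025^(1/n). With x = 3 the upper limit is the 97.5th percentile of Beta(x + 1, n − x).

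| Unexposed u | n = 150 + u | Upper limit, 0 events | Rate, 3 events | 95% limits, 3 events |
|---|---|---|---|---|
| 0 | 150 | 2.43% | 2.00% | 0.41% to 5.73% |
| 3 | 153 | 2.38% | 1.96% | 0.41% to 5.62% |
| 10 | 160 | 2.28% | 1.88% | 0.39% to 5.38% |
| 25 | 175 | 2.09% | 1.71% | 0.35% to 4.93% |

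With u = 25 the upper limit falls by 2.43 − 2.09 = 0.34 percentage points with no events, and by 5.73 − 4.93 = 0.80 points with three. With u = 3 the falls are 0.05 and 0.11 points.

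Protocol 10.5 names a score interval instead of Clopper-Pearson. The direction is the same: with three events the Wilson upper limit goes from 5.72% at n = 150 to 4.92% at n = 175.

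**Is the evaluable set the right replacement?** Not quite. It requires a cap applied. Protocol 7.5 provides for a connector on which no cap can be attached. A participant with only failed attempts was exposed to the device, could have a device-related event, and might be left out. The set needed is applied or attempted. SAP 5.3 already takes its cap totals from fields such as "PureHub Initial Placement page, Number of caps used" and its matching Maintenance-page field, and states that the total includes caps that were tried but did not attach. The set can therefore be built from data already collected.

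**The case against.** The strongest reply is that the effect may be negligible. Every participant is meant to receive a cap (Protocol 4.1 and 7.4), screen failures are not expected (Protocol 5.4), and placement can follow consent on the same day. One cap is enough to be exposed, so later withdrawal does not matter. The gap between 175 and 150 is an enrolment allowance. The documents do not say that 25 consented participants will go without a cap, and because 150 is a target it is not a strict bound either. This stands as a point about size; u = 25 is an illustration, not a forecast.

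A reader could also rebuild the figure. SAP 6.1 reports enrolled and evaluable counts, and Section 7 lists all AEs. That holds too, except for participants with only failed attempts, whom 6.1 does not count. It does not correct the headline estimate.

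The enrolled set is prespecified and cannot lose a participant whose caps would not attach. True, but an applied-or-attempted denominator keeps that participant as well.

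Two narrower points. Exclusion criterion 1 tolerates a cap in place for up to 12 hours before participation, so someone with no study cap might still have had prior exposure; a separate listing of events in never-exposed participants would show any such case. And Section 7 includes bloodstream infections whatever their cause, so the argument that an unexposed participant cannot have the event is weaker there. Using the same denominator is still reasonable, because no event is dropped from the listings.

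**Conclusion.** The concern holds. SAP 5.2 prescribes a denominator that may include people who never had contact with the device, and this can only lower a primary safety estimate or its upper limit. The direction is certain whenever at least one enrolled participant was unexposed; the size is not known. Under the assumed range the relative dilution is 0% to 14.3%, and the zero-event upper limit lies between 2.43% and 2.09%. The true effect may sit near the small end, and is nil if every consented participant had a cap applied or attempted. No pass/fail conclusion depends on it. It should be corrected because it concerns a primary endpoint, favours the device, and departs from how the SAP handles its other primary endpoints.

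**What to change.** In SAP 5.2, replace the population sentence with wording such as:

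> The denominator is all enrolled participants in whom at least one PureHub cap was applied or attempted, identified by a count of caps used of 1 or more on the Initial Placement or Maintenance CRF page. Any AE in an enrolled participant with no cap applied or attempted will be listed separately.

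Use the same denominator for the percentages in SAP Section 7, so that the two safety outputs agree, and keep the listings on the full enrolled set. Naming this denominator in Protocol 10.5 would be tidy but is optional: Protocol Section 10 leaves technical detail to the SAP, and a protocol amendment would need ethics committee notification and, where applicable, approval.

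The cost is one sentence in the SAP, a matching change in Section 7, and one derived flag from existing CRF fields. No new data are needed. The reported rate and upper limit become slightly less favourable, or stay the same if everyone enrolled was exposed.

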5.3 Informational Endpoint(s)

The informational endpoints are:

- The number of BD PureHub™ Disinfecting Caps used per day/per study participant
- The purposes for each intended removal of the BD PureHub™ Disinfecting Cap from the needle free connector
- Incidence of central line associated bloodstream infection (CLABSI)
- Incidence of bloodstream infections

The calculation of number of PureHub caps used per day will be total number of caps used (including the ones attempted but didn’t attach) divided by number of days participants were in VAD therapy. If multiple VADs were removed, number of days will be last VAD removal date – PureHub initial placement date. If at least one VAD is not removed, the number of days will be the minimum of study duration (participant end of study date – PureHub initial placement date) and 45 days. The number of caps used will be from the following CRF pages:

- PureHub Initial Placement page, Number of caps used
- PureHub Maintenance page, Number of caps used

The purposes of removal of the BD PureHub™ Disinfecting Cap are identified on “PureHub Maintenance” log in response to “Removal reason” question. The percentage of each response will be provided, and the denominator will be the total number of intended removals.

Incidence of bloodstream infections can be identified on the CRF “Adverse Events” log form. If response to “In case of bloodstream infection, how was it confirmed” is not “Blood Stream Infection Not Present”, then subject had a bloodstream infection.

Central line associated bloodstream infection can be identified if the response to “Is the bloodstream infection central-line associated” is “Yes” on the CRF “Adverse Events” log form.

The analysis will be performed on the evaluable population. Descriptive statistics for the informational endpoints will be provided. Summary statistics for categorical variables will include frequency counts and percentages and for continuous variables will include mean, standard deviation, minimum, median, and maximum.

6 Summary of General Study Data

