### 4.3 End of Study Definition

A participant is considered to have completed the study when one of the following conditions are met, whichever is the earliest.:

- upon one week post VAD therapy (after the last VAD is removed),
- at department discharge provided the clinical investigation team cannot follow-up the participant on another ward for study purposes,
- at hospital discharge provided participant, if VAD is still placed, will not return for catheter access to the site or,
- 45 days from enrollment

If a participant has more than one (1) VAD with eligible needle-free connectors at study start, data will be collected on each VAD and the end of study time point occurs when the last VAD is removed. If an additional VAD is placed at a later time point, or if one of these VADs is replaced, then the new VAD is excluded from the study.

The end of the study is defined as the date of the last study assessment of the last participant in the study.

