### 7.1 Study duration

The study participation per participant will last 45 days at maximum, the overall conduct of the study is expected to last approximately 14-15 months from first participant enrolled up to last participant having last visit, which is projected for ~ Q2 2023. The anticipated enrollment period is 13 months.

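### SAP 5.3 limits the days in caps per day to 45 but not the caps, so the rate can be wrong for any participant who overruns the protocol's 45-day stop

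*SAP*

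**What the plan says.** SAP 5.3 defines the rate as follows: "The calculation of number of PureHub caps used per day will be total number of caps used", including caps that were tried and did not attach, "divided by number of days participants were in VAD therapy". The caps come from the Initial Placement and Maintenance pages, and no date limit is stated for them.

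The days are set by two branches:

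- VADs removed: "If multiple VADs were removed, number of days will be last VAD removal date – PureHub initial placement date". There is no 45-day limit. The sentence speaks of several VADs; I read it as also covering a single removed VAD.
- A VAD still in place: "If at least one VAD is not removed, the number of days will be the minimum of study duration" and 45 days, where the two terms compared are "participant end of study date – PureHub initial placement date) and 45 days".

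The protocol's stop runs from a different date. Section 4.3 ends participation at the earliest of several events, one of which is "45 days from enrollment". Section 7.1 agrees: "The study participation per participant will last 45 days at maximum". Enrolment is the signing of consent (Protocol 4.1 and 7.2). The first cap may go on the same day or later: inclusion criterion 1 admits a participant whose device is still to be placed, and note 6 to Table 1 provides for a placement date that differs from baseline.

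The SAP revision history records that version 3.0 added the 45-day limit on days. It mentions no matching limit on caps.

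**The concern.** A rate needs its numerator and denominator to cover the same time. Here the denominator can be cut at 45 days while the numerator keeps every recorded cap. The cut applies in one branch only, so two overrunning participants with identical use can get different rates depending on whether the VAD came out. The cut also runs from first cap, while the protocol's stop runs from consent.

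At stake is the frequency-of-use endpoint, and within it only participants whose follow-up ran past the protocol window.

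**Working it through.** The documents state no caps-per-day figure, so there is none to reproduce.

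**Inputs.** From the documents: the 45-day limit from first cap (SAP 5.3), the 45-day stop from enrolment (Protocol 4.3 and 7.1), and first cap on or after consent (Protocol Table 1, note 1). Assumed, because the documents do not give them: the gap g from consent to first cap (0 to 7 days), the overrun k of recorded end of study beyond enrolment + 45, constant use of r caps per day, and the share of participants overrunning. The ratios below do not depend on r; r = 2 is used for illustration.

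Days from first cap to end of study are D = 45 + k - g. With a VAD in place, the SAP divides by min(D, 45).

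1. **Protocol stop kept (k ≤ 0).** D = 45 + k - g is at most 45, so min(D, 45) = D and the rate is rD/D = r. With g = 3 and k = 0, 42 days of caps are divided by 42 days. The limit never binds, and the different starting dates do no harm because the end of study date already carries the enrolment-based stop.

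2. **Overrun, VAD in place, caps recorded throughout.** Once D exceeds 45, the rate is rD/45, so it is too high by the factor D/45.
   - D = 48: 96/45 = 2.13, factor 1.067 (+7%)
   - D = 52: 104/45 = 2.31, factor 1.156 (+16%)
   - D = 60: 120/45 = 2.67, factor 1.333 (+33%)

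   A gap shortens D: with g = 3 and k = 7, D = 49 and the factor is 49/45 = 1.089. If k ≤ g, D is at most 45 and the rate is undistorted, although some use after the protocol window is counted.

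3. **Same participant, other branch.** At D = 52 with the VAD removed that day, the SAP gives 104/52 = 2.00, against 2.31 with the VAD still in.

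4. **End of study merely dated late; caps stopped at enrolment + 45.** Caps cover 45 - g days. Once the limit binds, the rate is r(45 - g)/45.
   - g = 0: 45/45 = 1.000. The limit helps here: with end of study dated day 52 and no limit, the ratio would be 45/52 = 0.865.
   - g = 3: 42/45 = 0.933 (-6.7%)
   - g = 7: 38/45 = 0.844 (-15.6%)

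5. **Cohort mean.** If all participants share the same r, g = 0, and a share s overruns by k days as in step 2, the mean rises by s × k/45.
   - 5% overrunning by 7 days: 0.05 × 7/45 = 0.0078 (+0.8%)
   - 10% overrunning by 15 days: 0.10 × 15/45 = 0.033 (+3.3%)

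6. **Matched window.** If caps and days are both cut at the earlier of end of study and enrolment + 45, the rate equals r in every case above.

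**The case against.** The strongest reply is that the protocol already prevents the problem. If the 45-day stop is kept, the limit in SAP 5.3 has no effect, and no overrun or late cap record appears anywhere in the documents. Where an end date is merely late and the first cap was on the consent day, the limit repairs the days. The removed-VAD branch returned the true rate in step 3. The derived data specification (SAP 3.2) is still to be finalised and could hold a date filter. Deviations are already to be recorded (Protocol 12.4) and listed (SAP 6.2). The endpoint is descriptive, with the median reported beside the mean, and SAP 2.8 sets no acceptance criteria.

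Most of this stands, and it rules out three stronger readings that a reader might infer:

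- That reported cap use is misstated in general. Step 1 shows that it is not when the protocol is followed.
- That counting from first cap biases the rate in itself. It does so only when the end date overruns, caps stopped at enrolment + 45, and there was a gap before first cap (step 4).
- That version 3.0 of the SAP shows overruns had been seen. The revision history gives no reason for the limit and no counts.

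What the reply does not remove is that the limit operates only on overruns, and there the text as written does not match caps to days. A later specification that followed SAP 5.3 literally would carry the mismatch forward.

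**Conclusion.** The point holds in a conditional form. SAP 5.3 states a rule that is harmless when the protocol stop is kept. When the limit does bind, then under constant use it gives the right rate only if the recorded caps span exactly 45 days from first cap. Otherwise the overrunning participant's rate is too high by the factor (days from first cap)/45 if caps continued, or too low by g/45 if caps stopped at enrolment + 45 and the first cap came g days after consent.

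The individual errors above rest on assumed overruns and gaps, and the cohort figures on assumed shares as well. The effect on the cohort mean is probably small. No primary endpoint uses this denominator. This is a minor improvement to an informational endpoint.

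**What to change.** In SAP 5.3, use one window in both branches: from initial placement to the earliest of last study-VAD removal, participant end of study, and enrolment date + 45 days. Count only caps dated within that window and divide by the days in that window. Cap records outside it can be listed with the protocol deviations already planned.

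Both parts must move together. Moving only the denominator to enrolment + 45 would make matters worse: with g = 3 and k = 3, 45 days of caps would be divided by 42 days, a factor of 45/42 = 1.071, where the present rule gives 1.000.

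The cost is a few words in SAP 5.3 and a date filter in the derivation. Consent date, VAD removal date, first placement and daily cap counts are already collected (Protocol 7.3 and Table 1). Trial conduct and the attachment and removal endpoints are unaffected.

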## Abbreviations

ADE	Adverse Device Effect
AE	Adverse event
BD	Becton Dickinson and Company
BSI	Blood Stream Infection
CE	Certification Mark
CI	Confidence Interval
CLABSI	Central Line Associated Blood Stream Infection Defined as a primary BSI with use of a central vascular catheter in the 48 hours (two days) before the onset of the infection
CRBSI	Catheter-related Bloodstream Infection Defined as the presence of bacteraemia originating from an intravenous catheter 
CSA	Clinical Study Agreement
CV	Curriculum Vitae
DEHP	Diethylhexyl Phthalate
DMP	Data Management Plan
eCRF	Electronic Case Report/Record Form
EEA	European Economic Area
EU	European Union
FDA	Food and Drug Administration
FDAAA	FDA Amendments Act of 2007
GCP	Good Clinical Practice
GDPR	General Data Protection Regulation
ICF	Informed Consent Form
ICH	International Conference on Harmonisation
ICMJE	International Committee of Medical Journal Editors
IFU	Instructions for Use
IPA	Isopropyl Alcohol
IRB/EC	Institutional or Independent Review Board/Ethics Committee
IV	Intravenous
LAR	Legal Authorized Representative
NDA	Non-disclosure Agreement
PI	Principal Investigator
SADE	Serious Adverse Device Effect
SAE	Serious Adverse Event
SIV	Site Initiation Visit
TMF	Trial Master File
UADE	Unexpected Adverse Device Effect
USADE	Unexpected Serious Adverse Device Effect
VAD	Vascular Access Device

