1.2 Objectives and Endpoints

Objectives	Endpoints
Primary Efficacy Objective	
To assess the rate of select performance measures of the BD PureHub™ Disinfecting Caps on swabbable needle-free connectors when used in a clinical environment.	
 ▪ Attachment success rate of the BD PureHub™ Disinfecting Caps to a needle-free connector (successful attachment/ total number of attachments) ▪ Removal success rate of the BD PureHub™ Disinfecting Caps to a needle-free connector (successful removal/ total number of intended removals)
Primary Safety Objective	
To assess the incidence of BD PureHub™ Disinfecting Cap device-related adverse events.	
 ▪ Rate of device-related adverse events
Informative Objectives	
To assess the frequency of BD PureHub™ Disinfecting Cap use To summarize the purposes for removal of the BD PureHub™ Disinfecting Cap from the needle-free connector To summarize the incidence of blood stream infection	
 ▪ The number of BD PureHub™ Disinfecting Caps used per day/per study participant ▪ The purpose for each intended removal of the BD PureHub™ Disinfecting Cap from the needle-free connector ▪ Incidence of central line associated bloodstream infection (CLABSI) ▪ Incidence of bloodstream infections

2 Study Description

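### SAP 5.3 reports CLABSI only as a percentage of all evaluable participants, including any with no central line; a central-line denominator and a supporting line-day rate should be added

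*SAP*

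**What the plan says.** The objective in SAP 1.2 is modest: "To summarize the incidence of blood stream infection". CLABSI and all bloodstream infection are its two endpoints.

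- **Who can be a case.** The protocol's abbreviation list describes CLABSI as follows: "Defined as a primary BSI with use of a central vascular catheter in the 48 hours (two days) before the onset of the infection". SAP 5.3 takes cases from a Yes answer on the Adverse Events log.
- **Who is in the study.** The note to the first inclusion criterion (Protocol 5.1) reads: "This covers all needle-free devices, including central venous catheters, peripheral IV catheters and arterial VADs".
- **Who is in the denominator.** SAP 5.3 puts all informational endpoints on one set: "The analysis will be performed on the evaluable population. Descriptive statistics for the informational endpoints will be provided". SAP 4.1 defines evaluable as "All enrolled participants who have at least 1 BD PureHub™ Disinfecting Cap applied", with no condition on line type. Categorical variables get counts and percentages. Protocol 10.6 adds nothing specific to CLABSI.
- **What other endpoints in SAP 5.3 get.** For removal purposes, "the denominator will be the total number of intended removals". Caps per day has a time denominator that runs to the last VAD of any type: "If multiple VADs were removed, number of days will be last VAD removal date", less the initial placement date. Where a VAD stays in, study duration is used, limited to 45 days.
- **Weight of the endpoint.** SAP 2.8 states: "There are no acceptance criteria for the study device".

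**The concern.** A participant with only a peripheral or arterial VAD adds one to the denominator but, on the protocol's definition, cannot add to the numerator through a study line. The CLABSI percentage therefore moves with the mix of line types at the sites as well as with infection risk under the cap. A reader who takes it as the risk for patients with a central line would read a figure that is too low whenever some participants have none and at least one case occurs.

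Time is a second, lesser matter. Follow-up ends one week after VAD therapy, at discharge or at 45 days (SAP 2.1), so central-line time will differ between participants, and a percentage does not reflect it. This has no fixed direction of bias.

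At stake is how an infection figure is read in a study meant to supply clinical data under EU regulation 2017/745. The primary performance and safety results are not affected.

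**Working it through.** **Plan figures.** Neither document states a figure for CLABSI. The nearest is the sample-size statement on a rare event per participant (SAP 2.4), and it reproduces: 1 − 0.99^150 = 77.9% (stated 78%) and 1 − 0.98^150 = 95.2% (stated 95%). It does not bear on the CLABSI denominator. The planned number of evaluable participants, 150, comes from SAP 2.1.

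**Assumed inputs.** The central-line share s, the number of CLABSIs x and the mean central-line days are not in the documents. All are illustrative.

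**Step 1: dilution.** If every counted case is in a participant with a central study VAD, then

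planned percentage = x/150 = s × [x/(150s)] = share × risk among central-line participants.

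With x = 2 the planned figure is 2/150 = 1.33% at every share.

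| Share s | Central-line participants (150s) | 2/(150s) | Ratio to planned (1/s) |
|---|---|---|---|
| 100% | 150 | 1.33% | 1.00 |
| 90% | 135 | 1.48% | 1.11 |
| 75% | 112.5 | 1.78% | 1.33 |
| 50% | 75 | 2.67% | 2.00 |
| one third | 50 | 4.00% | 3.00 |

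Lower shares dilute more: the ratio is 4 at 25% and 10 at 10%. At 100% there is no dilution.

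**Step 2: zero events.** Both estimates are 0%. The exact two-sided 95% upper limit is 1 − 0.025^(1/n): 2.4% for n = 150 and 4.8% for n = 75. SAP 5.3 plans no interval for this endpoint; the limits show only what a 0% result could support on each denominator.

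**Step 3: line-days.** Take x = 2 in 75 central-line participants, which is 2.67% at any duration. The exact Poisson 95% limits for 2 events are 0.242 and 7.225. Dividing by line-days and multiplying by 1,000:

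| Mean central-line days | Line-days | Per 1,000 | 95% CI |
|---|---|---|---|
| 7 | 525 | 3.8 | 0.46 to 13.8 |
| 14 | 1,050 | 1.9 | 0.23 to 6.9 |
| 21 | 1,575 | 1.3 | 0.15 to 4.6 |

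**Step 4: can the caps-per-day days be reused?** Not for participants with mixed VADs. Suppose the 75 average 14 days to the last VAD of any type, 75 × 14 = 1,050 days, and half have the central line out 7 days earlier. Central-line days are 1,050 − 37.5 × 7 = 787.5. The rate is 2/787.5 = 2.5 per 1,000 on central-line days and 2/1,050 = 1.9 on caps-per-day days.

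**The case against.** The strongest reply is that nothing in the plan is wrong. The objective is only to summarise incidence, the population is named, and neither document presents the percentage as risk among central-line participants. The study is single-arm with no acceptance criterion and no planned CLABSI comparison. This stands: CLABSI per cap-exposed participant is a legitimate description, and a reader who infers that the planned figure is an error goes further than the documents allow.

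Second, the table shells in Appendix 1 are not shown, and SAP 3.2 leaves derived-data specifications until before reporting. Either might hold a central-line subset. This also stands as a limit: one cannot say that no such summary is intended, only that the SAP text does not provide for it.

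Third, the removal-purpose denominator is weak evidence of an oversight, since that endpoint counts removals and CLABSI is a yes/no per participant. That is fair; the point does not depend on it.

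Fourth, few or no events are likely, so the added rate may say little. With 525 line-days, the chance of no event is exp(−0.525) = 59%, exp(−1.05) = 35% or exp(−2.1) = 12% at assumed rates of 1, 2 or 4 per 1,000. Hence the line-day rate is only a supporting summary.

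Fifth, VAD types are tabulated at baseline (SAP 6.4) and all adverse events are listed (SAP 7). A reader could therefore approximate the central-line proportion, though not the line-days.

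**Conclusion.** The point holds as an inexpensive improvement to an informational endpoint. As written, SAP 5.3 gives CLABSI as a percentage of a population that may include participants with no central line. If it does, and at least one CLABSI occurs, the figure is about the central-line share times the risk among central-line participants: 1.3% against 2.7% with an assumed 2 events and a 50% share. With no events the estimates agree at 0% and only the upper limit differs, 2.4% against 4.8% at that share.

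The true size is unknown because the share and the event count are not in the documents. The relation is approximate because a case could arise on a central line placed later, which Protocol 4.3 excludes from the study.

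Two stronger readings are not supported. One is that ignoring line time biases the result in a known direction: it does not, it only leaves differing durations out of account. The other is that the study's conclusions are at risk: the primary endpoints do not use this denominator.

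**What to change.** In SAP 5.3, keep the planned percentages for CLABSI and for all bloodstream infection on the evaluable population, and state that denominator for CLABSI. List which recorded VAD types count as central. Then add:

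- (a) CLABSI, count and percentage, among evaluable participants with at least one central study VAD;
- (b) as a supporting summary, CLABSI per 1,000 central-line days with an exact Poisson 95% CI. Days run from initial PureHub placement to removal of the last central study VAD or end of study, capped at 45 days as SAP 5.3 already does for caps per day.

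Keep the existing case rule: a Yes on the Adverse Events log and the protocol's 48-hour definition. Do not require each case to be attributed to a particular study VAD. That would be a new case criterion, and the documents do not show that the CRF links an event to a line. Leave in the planned percentage, but list separately from (a) and (b), any CLABSI in a participant with no central study VAD, or with onset more than 48 hours after the last central study VAD was removed.

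The cost is SAP wording, two summaries and one derived variable, central-line days. VAD type and insertion and removal dates are already collected per VAD (Protocol 7.3). The onset date is assumed to be on the adverse event form, since the 48-hour definition cannot be applied without it. The downside is a smaller denominator and wide intervals when events are few.
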